Peer support: Therapeutic groups are a mainstay of addiction treatment because they offer drug users, who are often socially isolated, validation and support from others with similar experiences. The behavioral specialist will facilitate conversation about current opioid use, goals for recovery, and triggers for relapse. We anticipate this will take 20-25 minutes.

Medical Management: Each visit will end with guided relaxation and meditation as a way to calm any heightened emotions from group interactions. The physician will write prescriptions for BMT and address individual concerns (e.g., changes in buprenorphine dosage). Because group medical visits will replace most individual visits, focused histories and physical exams may be necessary and could occur in a private room as needed. If more attention is required for acute symptoms an individual visit can be scheduled at the CHC.

Interaction between primary care physicians (PCPs) and research team: The protocol for communications with referring PCPs will be as follows: 1) G-BMT participants will sign a treatment agreement stating that they will attend group visits weekly and all medication refill requests will go to the group physician; 2) the group physician will send electronic medical record (EMR) messages to the PCP with updates to the treatment plan following each group visit; 3) participants will continue to see their PCP for acute medical care, but not for BMT during the study period; and 4) the group physician will transfer care back to the PCP following completion of the G-BMT intervention through an in-person conversation. The treatment agreement (see appendix), which includes patient and provider expectations, and specifies that all prescriptions will be written at BMT group medical visits, will be discussed at the first group visit and signed by both patients and the G-BMT physician. Subsequently, PCPs will be asked to read and sign the agreement as well. Because this study is developmental, deviations from the agreement (e.g. asking the PCP for a prescription refill following a missed group visit) will be recorded as an outcome for future adaptations to the protocol.

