- a.) *Retention in treatment* will be used to determine whether participants remain in BMT following the specified time intervals. *Three month retention* will be defined as having a medical visit or active

buprenorphine prescription 12-16 weeks after study initiation (one month after G-BMT intervention completion). *Six month retention* will be assessed at 24-28 weeks after study initiation.

b.) *Changes in HIV risk behaviors* will be based on the AIDS risk inventory, which includes questions regarding frequency of injection drug use, number of times sharing syringes, number of sexual partners, and frequency of unprotected sex. We will assess risk behaviors at completion of the G-BMT intervention (8 week visit) and two months following completion of the intervention (16 week visit).

Primary outcome (acceptability): Overall satisfaction with BMT will be measured on a 5-point Likert scale for participants and providers.

Primary outcome (feasibility): We will compare *medication and visit adherence* between the G-BMT and TAU arms as the primary measure of feasibility. Medication adherence will be determined from medical record data based on lapses in BMT defined as the number of days without an active buprenorphine prescription during the study. Visit adherence will be defined as the proportion of obligated medical visits (as per G-BMT or TAU protocol) attended. Other important measures of feasibility are listed in Table 2 and will be used as secondary outcomes and to assess fidelity to the G-BMT intervention.

G-BMT component	Measure	Assessment
Overall	Participant engagement # urine drug tests collected Time per group medical visit	RA conducted EMR Timed
Buprenorphine Education	Fidelity to intervention Time for education	Checklist Timed
Self-management skills	Self-assessment forms Fidelity to intervention Time for instruction	Collected Checklist Timed
Peer Support	Personal Updates Feedback to other participants Group Cohesion Time for facilitated discussion	RA observed RA observed GCQ-S* Timed
Medication Management	# non-BMT medical complaints # individual physical exams Time for medical management	EMR RA observed Timed
*assessed as part of ACASI interviews		

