Outcome Measures: **Primary outcome (efficacy):** we will use a dichotomous measure (yes/no) of *opioid abstinence* based on 30-day self-reported opioid use following completion of the intervention and the results of urine drug tests (opiates, methadone, oxycodone) at the 8 and 12 week research visits. Missing urine drug tests will be considered to be positive for opioids.

Secondary outcomes (efficacy): 1.) *Retention in treatment* will be used to determine whether participants remain in BMT following the specified time intervals. *Three month retention* will be defined as having a medical visit or active buprenorphine prescription 12-16 weeks after study initiation (one month after G-BMT intervention completion). *Six month retention* will be assessed at 24-28 weeks after study initiation.

2.) *Changes in HIV risk behaviors* will be based on the AIDS risk inventory, which includes questions regarding frequency of injection drug use, number of times sharing syringes, number of sexual partners, and frequency of unprotected sex. We will assess risk behaviors at completion of the G-BMT intervention (8 week visit) and two months following completion of the intervention (16 week visit).

Primary outcome (acceptability): Overall satisfaction with BMT will be measured on a 5-point Likert scale for participants and providers.

Primary outcome (feasibility): We will compare *medication and visit adherence* between the G-BMT and TAU arms as the primary measure of feasibility. Medication adherence will be determined from medical record data based on lapses in BMT defined as the number of days without an active buprenorphine prescription during the study. Visit adherence will be defined as the proportion of obligated medical visits (as per G-BMT or TAU protocol) attended. Other important secondary outcomes will be measures of feasibility from assessments of fidelity to the G-BMT intervention based on audio-recordings and observations of the group medical visits.

Inclusion/exclusion criteria: 1) Currently receiving BMT at the CHC; 2) Received BMT for ≥ 12 weeks; 3) Persistent opioid abuse (urine drug testing positive for an unprescribed opioid in the previous 6 months); 4) ≥ 18 years old; 5) fluent in English or Spanish. Pregnant women and patients who show contraindications to BMT (alcohol use disorder; benzodiazepine use disorder; unstable mental health condition) will be excluded.

TRIAL MANAGEMENT

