Interview data will be collected via audio computer-assisted self-interview (ACASI) technology at baseline and during research visits 2, 4, 6, 8, 12, and 16 weeks following enrollment. *Urine samples* will be collected for drug testing at baseline and during research visits 2, 4, 6, 8, 12, and 16 weeks following enrollment. Urine drug tests will be conducted at the community health center using commercially available rapid urine drug test. At these research visits, the RA will ask subjects to provide a urine specimen in a private bathroom while the RA stands outside the door listening for tampering. Results of urine drug tests will be recorded on a standardized paper form only using the participants study ID and not other personal identifiers. *Feasibility* measures will be collected by the research assistant (RA) who will observe, time, and collect written intervention materials (e.g. self-assessment forms) from group visits. We plan to run 5 cycles of group visits, therefore, these field notes will be marked with the cycle number and group visit number but will not contain participant identifiers. *Written intervention materials* will be marked only with a study ID and transported directly to the research offices following weekly meetings between [name] (PI) and the research team. Materials will be stored in locked file cabinets. *Audio recordings* of each group visit and qualitative interviews will be collected by the RA using a digital audio-recording device. After each group visit or qualitative interview, audio recordings will be transferred to a single password protected encrypted computer and then erased from the recording device. Audio recordings will be uploaded to a secure internet portal for professional transcription and then will be transcribed with blinding of any references to personal identifiers.

Medical record data will be electronically extracting from Montefiore's centralized clinical database, and will include buprenorphine prescription data, and data on clinical visits (medical and counseling) and chronic health conditions. The electronic file will be created by Montefiore health technology staff, emailed to the PI in a password protected file, and saved on an encrypted password protected computer.

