Einstein IRB for review and approval prior to implementation. Any protocol deviations will be reported to the Einstein IRB within 10 days on a standard IRB protocol deviation reporting form, and corrective action will be implemented as necessary. Reports to the data safety monitoring committee will occur every six months and will include information about any amendments to the protocol and any protocol deviations. Amendments to the protocol will be reported to the Program Officer at NIDA in annual progress reports.

Trial stopping rules: Interim analysis of the data will be conducted when 50% of the sample has accrued (N = 40). If the results show overwhelming, statistically significant differences in opioid abstinence or retention in treatment between the intervention and TAU arms, the study will be stopped. If we find that buprenorphine treatment discontinuation or serious adverse events are significantly more likely in the TAU arm compared to the G-BMT arm (e.g., if primary care providers stop buprenorphine treatment because of persistent opioid abuse), the randomized study will be halted. If the study is halted due to the results of an interim analysis, the study may still continue as a one-arm trial (e.g., all subjects will participate in the G-BMT intervention until 80 participants have enrolled) in order to collect additional process measures on conducting group visits.

Interim analyses will be conducted by [name] with close feedback from the biostatistician. The research team, in collaboration with the DSMC and the Program Officer of NIDA will review all pertinent data to determine whether to continue accrual. A decision to stop the study may be made at any time that the research team and DSMC agrees that an unacceptable type and/or frequency of adverse events has been observed. [name] will report the decision to terminate the study to the DSMC, IRB and NIDA within 48 hours of this determination. He will submit a narrative description of the reasons for early termination of the study to the IRB and NIDA within 10 days.

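### Retention in BMT can be met by a medical visit that is not tied to BMT, so some participants without a buprenorphine prescription may count as retained

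*Combined protocol and SAP*

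**What the plan says.** The protocol defines retention in two places: under Secondary outcomes (efficacy) in section III (Analysis), and under Outcome Measures in section IV (Data and Safety Monitoring Plan). Both give the purpose first: retention "will be used to determine whether participants remain in BMT following the specified time intervals". Both then give the rule: three-month retention "will be defined as having a medical visit or active buprenorphine prescription 12-16 weeks after study initiation". Six-month retention "will be assessed at 24-28 weeks after study initiation" and has no criterion of its own, so the same either/or rule presumably carries over.

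Four other places bear on how the rule would work:

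- **Interaction between primary care physicians (PCPs) and research team.** In the group arm (G-BMT), "participants will continue to see their PCP for acute medical care, but not for BMT during the study period". After the eight weekly sessions, "the group physician will transfer care back to the PCP following completion of the G-BMT intervention".
- **Data acquisition and transmission.** The record extract holds buprenorphine prescriptions and "data on clinical visits (medical and counseling) and chronic health conditions". No filter by reason for visit is stated.
- **Treatment as usual; Continuing BMT despite ongoing opioid abuse; Trial stopping rules.** These foresee participants leaving buprenorphine, through referral to another program or because a PCP stops it.
- **Trial stopping rules; Interim analysis of efficacy data.** The study stops if the half-way analysis shows "overwhelming, statistically significant differences in opioid abstinence or retention in treatment between the intervention and TAU arms".

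**The concern.** The purpose and the rule do not match. The purpose concerns one treatment. The rule accepts a visit of unspecified type, at a clinic that also gives general and specialist care.

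The visit route changes the classification only of participants who have no active prescription in the window, and these are the people the outcome has to identify. Someone transferred to a methadone program who sees the PCP about something else in week 14 would be retained in BMT on the literal text. Under the stopping rules, which treat buprenorphine discontinuation as a separate criterion, that participant could be both discontinued and retained.

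At stake are a true difference in retention that would look smaller than it is, an interim criterion that rests on the same measure, and a diluted estimate passed on to the larger trial this pilot is meant to inform.

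**Working it through.** **1. The plan's own figure.** No power or expected rate is given for retention. The only power figure is for abstinence: 40 per arm, 10% in the control arm, intra-class correlation 0.01, 80% power, detectable rate 37%. With groups of eight the design effect is 1 + (8 − 1) × 0.01 = 1.07, so the effective size is 40 / 1.07 = 37.4 per arm. Assuming a two-sided 5% level (none is stated) and a pooled normal approximation, power at 10% versus 37% is 79.9% and the detectable rate is 37.1%. The plan's figure reproduces, and this point does not affect it.

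**2. Who can be misclassified under the literal rule.**

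| Active prescription in window | Unrelated visit in window | Rule gives | In BMT? |
|---|---|---|---|
| Yes | Yes or no | Retained | Yes |
| No, and no BMT visit | No | Not retained | No |
| No, and no BMT visit | Yes | Retained | No |

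Only the last row is wrong.

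**3. Effect on the arm difference.** Let r be the true proportion in BMT in the window, and v the chance that a participant not in BMT has an unrelated visit in it. Then

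observed retention = r + (1 − r)v.

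With the same v in both arms,

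observed difference = (r₂ − r₁)(1 − v).

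Inputs: r₁ = 60% and r₂ = 80% are assumptions, chosen inside the 59–93% range that the Background reports for primary care. The documents give no v, so a range is shown.

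| v | Lower arm | Higher arm | Difference |
|---|---|---|---|
| 0 | 60% | 80% | 20 points |
| 0.1 | 0.60 + 0.40 × 0.1 = 64% | 0.80 + 0.20 × 0.1 = 82% | 18 points |
| 0.3 | 0.60 + 0.40 × 0.3 = 72% | 0.80 + 0.20 × 0.3 = 86% | 14 points |
| 0.5 | 0.60 + 0.40 × 0.5 = 80% | 0.80 + 0.20 × 0.5 = 90% | 10 points |
| 0.7 | 0.60 + 0.40 × 0.7 = 88% | 0.80 + 0.20 × 0.7 = 94% | 6 points |

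In counts, with 40 per arm, 16 and 8 participants are truly out of BMT. At v = 0.5, 8 and 4 of them are moved to retained.

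**4. Effect on power, in a second illustration.** Take assumed true rates of 59% and 85%, an effective 37.4 per arm, and the method of step 1 (borrowing the abstinence intra-class correlation). Power is 71.5% at v = 0, 65.0% at v = 0.10, 54.5% at v = 0.25, 36.5% at v = 0.50 and 19.3% at v = 0.75.

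**5. Is the visit limited to BMT anywhere?** Where the plan wants the limit it can state it: the Treatment as usual section speaks of BMT visits, and visit adherence counts the visits that each arm's protocol requires. The retention rule has no such words. Table 1 calls the measure retention in care, which leans toward the broader reading.

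**The case against.** The strongest reply is that a medical visit here means a BMT visit. The sentence follows directly on one about remaining in BMT. The documents often use the term that way, for example for the clinic visits of both arms at which urine is tested, and for the visits counted as observed BMT intensity in the TAU arm. This stands as a plausible account of intent. It does not settle the rule, because an analyst working from the extract is given no basis for leaving other visits out.

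The supporting evidence also has limits. The statement about acute care concerns the G-BMT arm while the group physician prescribes, and care has gone back to the PCP before week 12. It shows that non-BMT visits occur at this site, not how often participants off buprenorphine make them in the window. The Background says that many patients who do not reach abstinence drop out of care altogether, which would make v small.

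A reader might infer that the rule could create a false difference, because TAU physicians work under at-least-monthly visits with e-mail reminders. The documents do not support this. That visit rule covers BMT patients, whereas v concerns people no longer in BMT, and by weeks 12–16 the PCP provides BMT in both arms. Nothing in the documents gives a reason for v to differ by arm.

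A reader might also infer that the rule makes a wrongful efficacy stop more likely. With equal v, dilution makes a stop triggered by retention less likely, and discontinuation has its own halting criterion.

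Finally, days without an active prescription are compared between arms. This covers part of the construct, but as a feasibility measure and not as the retention outcome.

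**Conclusion.** The point holds as a defect of definition in a secondary efficacy outcome. As written, the rule can count participants without an active prescription as retained in BMT, in the three-month window and presumably in the six-month one.

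It would go too far to say that the outcome fails to measure retention. The measure is contaminated, and the error is confined to an unknown share of participants without a prescription. With equal v the true difference is multiplied by 1 − v: in the 60% versus 80% illustration, a loss of 2 points at v = 0.1 and 14 points at v = 0.7. Those sizes rest on assumed retention rates, an assumed v and the literal reading of the visit route. If only BMT visits were meant, the loss disappears, but the sentence still needs the words. The change should be made, because the outcome is named in the interim rule and the correction is cheap.

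**What to change.** In both places where retention is defined, replace the rule with one that covers both windows, for example:

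> Retention at three months (weeks 12–16) and at six months (weeks 24–28) requires a record, within that window, of an active buprenorphine prescription or of a visit documented as a BMT visit.

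Then:

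- Delete the unqualified medical-visit route.
- State whether a prescription active on any single day of the window is enough, since one ending early in week 12 would otherwise be open to argument.
- Refer to this definition wherever retention appears in Trial stopping rules and Interim analysis of efficacy data.
- Report the current either/or rule as a supportive analysis, so that its effect can be seen.

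The cost is a few sentences of text and some extra coding of the planned record extract to mark BMT visits. Prescription data are already in that extract. Table 1 lists prescriptions and visits only for weeks 1–16, so the sponsor should confirm that the extract reaches week 28, which either definition needs. Reported retention will be somewhat lower than under the current rule.

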Einstein IRB for review and approval prior to implementation. Any protocol deviations will be reported to the Einstein IRB within 10 days on a standard IRB protocol deviation reporting form, and corrective action will be implemented as necessary. Reports to the data safety monitoring committee will occur every six months and will include information about any amendments to the protocol and any protocol deviations. Amendments to the protocol will be reported to the Program Officer at NIDA in annual progress reports.

Trial stopping rules: Interim analysis of the data will be conducted when 50% of the sample has accrued (N = 40). If the results show overwhelming, statistically significant differences in opioid abstinence or retention in treatment between the intervention and TAU arms, the study will be stopped. If we find that buprenorphine treatment discontinuation or serious adverse events are significantly more likely in the TAU arm compared to the G-BMT arm (e.g., if primary care providers stop buprenorphine treatment because of persistent opioid abuse), the randomized study will be halted. If the study is halted due to the results of an interim analysis, the study may still continue as a one-arm trial (e.g., all subjects will participate in the G-BMT intervention until 80 participants have enrolled) in order to collect additional process measures on conducting group visits.

Interim analyses will be conducted by [name] with close feedback from the biostatistician. The research team, in collaboration with the DSMC and the Program Officer of NIDA will review all pertinent data to determine whether to continue accrual. A decision to stop the study may be made at any time that the research team and DSMC agrees that an unacceptable type and/or frequency of adverse events has been observed. [name] will report the decision to terminate the study to the DSMC, IRB and NIDA within 48 hours of this determination. He will submit a narrative description of the reasons for early termination of the study to the IRB and NIDA within 10 days.

Disclosure of conflict of interest: Prior to IRB approval and protocol initiation, all key personnel are required to disclose any financial interest that they, their partners, or their dependent children have related to the research or its sponsor. Potential financial interests include anything of monetary value, including cash, stocks or other ownership interests, and patents, copyrights, or other property rights. Key personnel are instructed to notify the Einstein IRB promptly if a change in conflict of interest occurs during the course of the study and are queried on changes every 90 days. Potential conflicts of interest are also reassessed annually during annual progress reports to the Einstein IRB.

TRIAL SAFETY

Potential risks for participants: The primary risks of this study are: (1) Breach of confidentiality leading to embarrassment or dismissal from buprenorphine treatment program; (2) inconvenience and discomfort associated with interviews or urine drug testing; (3) fear that refusal to participate will affect care at the healthcenter; (4) stress imposed participants due to group interactions; (5) continuing BMT despite ongoing opioid abuse; (6) burden of

attending an increased number of medical visits following intensification of BMT

Confidentiality issues: We will collect personal information from participants to facilitate tracking, and we will be asking personal questions including substance use and HIV risk behaviors. We have outlined our procedures to maintain confidentiality below.

Inconvenience and discomfort associated with interviews or urine drug testing: Participants will be asked about substance use, psychosocial distress, and opioid addiction treatment. Urine drug testing will be conducted by research staff. It is possible that such questions and procedures could produce anxiety in participants.

Fear that refusal to participate will affect care or services: Participants must have a doctor at Montefiore's community health center as part of inclusion criteria. In the informed consent process, they will be clearly instructed that refusal to participate will in no way affect their care at the affiliated health center.

Stress imposed on participants due to group participation: There will be a board certified physician and behavioral specialist at each group medical visit. Drs. [name] and [name] will also be available to intervene if participants express high levels of distress during group medical visits. Drs. [name] and [name] will review audio recordings of group sessions and have regular meetings with study clinicians to inquire about distress or conflict during group sessions.

Continuing BMT despite ongoing opioid abuse: We are selecting for a population with persistent opioid abuse, and these individuals may need a higher level of treatment intensity than can be offered in primary care settings.

Burden of attending an increased number of medical visits following intensification of BMT: Participants randomized to the G-BMT intervention will be expected to attend weekly group visits during the 8 week intervention. Participants randomized to the TAU arm will also likely be required to attend an increased number of medical visits, because PCPs will follow an intensification of BMT protocol that instructs them to increase visits to twice monthly or weekly if participants continue to abuse opioids. The increased number of visits could be burdensome and negatively affect adherence to buprenorphine treatment if participants missed medical visits and had lapses in their buprenorphine prescriptions.

Recruitment and informed consent: We will obtain informed consent for all participants of the RCT prior to collecting any information with personal identifiers (e.g. locator form or medical record release forms), administering the baseline ACASI interview, and randomization to an intervention arm. Informed consent will be obtained by the RA.

Protection against risk: We will institute the following processes to ensure confidentiality is maintained:

We will create a system that prevents linking sensitive material to participants' personal identifiers. We will have a "name-based" system and "ID-based" system that will remain all documents that have patient identifiers will be filed together. Some of these documents will have participants' signatures (e.g. consent forms) and others will have personal information (e.g. locator forms).

In the ID-based system, all documents that do not include identifying information or signatures will use participants' IDs (rather than names), and will be filed together. All forms will contain either participants' names or their study IDs, but not both. We will maintain one electronic document that links participants' names and study IDs, which will be stored on a password-protected computer.

1. We will obtain a Certificate of Confidentiality to protect participants' sensitive information.
2. Letters and/or phone messages that are left for participants (reminders of group medical visits or to schedule research visits) will not include any personal identifying information, and will not mention buprenorphine treatment.
3. Study records will be kept in locked files and/or within limited access, password-protected computer files, available only to the investigators and study personnel.
4. Publication or presentation of study results will not identify subjects by name.

Management of inconvenience, discomfort, and distress: In addition to addressing issues of confidentiality, it is crucial that we protect participants from psychological distress that may occur during any of the intervention or research activities. Participants will be instructed that they may withdraw from the study if this occurs. [name] will be contacted by cell phone if any study participants become overly distressed. [name] (a board-certified general internist) will be involved with all study activities and will assess for severe discomfort or other severe problems. [name] (a clinical psychologist) will also be available to assess participants with high levels of distress. Depending on severity of the problem, participants may be escorted to either Montefiore's community health center or emergency department. Participants may be referred for individual medical or psychiatric attention at Montefiore's community health center or the emergency department (depending on severity).

Continuing BMT despite ongoing opioid abuse: Participants with three consecutive urine drug tests that are positive for opioids during group medical visits will be offered facilitated referral to methadone maintenance treatment program; however, some may refuse referral. In the G-BMT intervention arm, the research team will meet to discuss the risks and benefits of continuing BMT and participation in group medical visits. In the TAU arm, continuation of BMT will be up to the prescribing physician. If there is concern that risks of continuing treatment outweigh the potential benefits, the participant will be removed from the trial and referred to an

addiction specialist.

Burden of BMT intensification: We will collect data on adherence to medication and visits as a feasibility measure, and we will monitor treatment, after 50% of the sample has accrued.

Potential benefits for participants: Group visits have the potential to improve rates of opioid abstinence thereby reducing HIV risk behaviors and overdose risk. Our preliminary work on buprenorphine group visits has demonstrated that they are highly valued, therefore, other benefits, such as reductions in depressive symptoms or distress, may lead to improved health status.

Collection of AEs and SAEs: Because the research visits will include computerized interviews and urine collection, and the G-BMT intervention will include group counseling and buprenorphine education, participants are likely to incur no more than minimal risk of AEs. However, if AEs occur, they are likely to include psychological distress. AEs will be collected by members of the research team as they conduct research visits or group visits, and will be reported to [name] either immediately (for serious AEs) or during regular weekly project meetings (for non-serious AEs). Serious AEs could include death, life-threatening adverse reaction, inpatient hospitalization, persistent disability, or an event jeopardizing the participant's health.

